## 2 LIST OF ABBREVIATIONS

AE	Adverse Event
AESI	Adverse Event of Special Interest
AR	Adverse Reaction
ARR	Annualized Relapse Rate
CTCAE	Common Terminology Criteria for Adverse Events
DMD	Disease Modifying Drug
DMT	Disease Modifying Therapy
eCRF	Electronic Case Report Form
EDSS	Expanded Disability Status Scale
EOS	End of Study Visit
HIV	Human Immunodeficiency Virus
ICF	Informed Consent Form
IEC	Independent Ethics Committee
MAH	Marketing authorization holder
MRI	Magnetic Resonance Imaging
MS	Multiple Sclerosis
NEDA	No evidence of disease activity
PML	Progressive Multifocal Leukoencephalopathy
PW	Premature Withdrawal
RRMS	Relapsing Remitting Multiple Sclerosis
SAE	Serious Adverse Event
SAR	Serious Adverse Reaction
SAP	Statistical Analysis Plan
SmPC	Summary of Product Characteristics
SPMS	Secondary Progressive Multiple Sclerosis

## 3 INTRODUCTION AND RATIONALE

Number of available disease modifying treatments (DMT) for patients with multiple sclerosis (MS) increased considerably in the past decade, however treatment responses are often less than complete, and concern regarding safety and side effect profiles may limit the general use of these drugs. The need for parenteral administration may present relative or absolute barriers to access, limiting treatment adherence and long-term outcomes.

Cladribine 10 mg tablets (MAVENCLAD®) is a novel oral disease modifying drug (DMD) approved in European Union for the treatment of adult patients with highly active relapsing multiple sclerosis.

Cladribine is a nucleoside analogue of deoxyadenosine, which preferentially depletes lymphocytes by exploiting the kinase-to-phosphatase enzyme profile in these cells. This produces moderate and discontinuous reductions in T and B cells with relatively minor and transient effects on innate immune cells, such as neutrophils and monocytes. The dosing regimen of cladribine tablets involves very short treatment periods relative to the length of

clinical effect to moderate lymphopenia, reflecting the cladribine mode of action (Mavenclad Summary of Product Characteristics – SmPC, 2018).

To achieve disease control over 4 years with Cladribine 10 mg tablets (Giovannoni et al., 2018), a maximum of 20 days of oral dosing in the first 2 years is needed with no further treatment required in the next 2 years. Each treatment course consists of 2 treatment weeks, one at the beginning of the first month and one at the beginning of the second month of the respective treatment year. Each treatment week consists of 4 or 5 days on which a patient receives 10 mg or 20 mg (one or two tablets) as a single daily dose, depending on body weight (MAVENCLAD SmPC, 2018).

**Table 3-1: Schedule of Cladribine 10 mg tablets dosing and lymphocyte count monitoring per SmPC**

	Pre-dose	Month 1	Month 2	Month 3	Months 4-6	Month 7	Months 8-12
Year 1	Lymphocyte count	maximum 5 day dosing	maximum 5 day dosing	Lymphocyte count		Lymphocyte count	
Year 2	Lymphocyte count	maximum 5 day dosing	maximum 5 day dosing	Lymphocyte count		Lymphocyte count	
Year 3							
Year 4							

In terms of efficacy, Cladribine 10 mg tablets has consistently shown robust clinically and statistically significant benefits in subjects across the spectrum of RRMS (early to late stages, treatment naïve or experienced subjects) (Giovannoni et al., 2010; Leist et al., 2014) with improvements in both clinical and radiological efficacy outcomes. In particular, it was found that treatment with oral Cladribine 10 mg tablets resulted in significant improvements in the annualized relapse rate (ARR) with significantly more subjects remaining free from relapse, free from 3-month sustained Expanded Disability Status Scale (EDSS) progression and free from magnetic resonance imaging (MRI) lesion activity over 96 weeks compared to placebo (Giovannoni et al., 2010).

Furthermore, safety and tolerability profile of Cladribine 10 mg tablets is favourable and well characterized as resulted from extensive clinical study experience, namely with 3 Phase III studies (CLARITY, ORACLE and ONWARD) and an 8-year safety registry (PREMIERE) (Giovannoni et al., 2010; Comi et al., 2018; Leist et al., 2014; Montalban et al., 2018; Cook et al., 2019).

Since none of cladribine clinical studies has been conducted in Slovakia to date, efficacy and safety data from this country are missing. The aim of the present study is to evaluate clinical benefits of Cladribine 10 mg tablets treatment in real-life settings of Slovakian clinical practice as this information is standard requirement of health authorities and payers and is especially demanded by local medical community. Due to specific prescribing limitation issued by Slovakian Ministry of Health (as described in Inclusion criteria), there is no possibility to extrapolate such data from any other European country. Except relapse and disability progression rate assessment as key effectiveness parameters, change of EDSS, patient adherence and safety data will be evaluated in this CLASS study.

## 4 STUDY OBJECTIVES

### 4.1 Primary

- To assess the effectiveness of Cladribine 10 mg tablets in the real life settings by the ARR^3 during the 4-year observational period.

### 4.2 Secondary

- To evaluate disability progression occurrence during the 4-year study observational period.
- To evaluate changes of EDSS during the 4-year study observational period.
- To evaluate the MRI measures performed yearly during the 4-year study observational period.
- To evaluate the proportion of patients receiving rescue therapy according to the local standards of care during the 4-year observational period.
- To evaluate the patient adherence to Cladribine 10 mg tablets treatment after both dosing periods in year 1 and 2.
- To evaluate association of patient adherence to treatment with relapse occurrence during the 4-year study observational period.
- To evaluate safety of Cladribine 10 mg tablets treatment during the 4-year study observational period.

---

 A relapse is defined as meeting the following criteria:

4. Neurological abnormality, either newly appearing or re-appearing, with abnormality specified by both
  - a. Neurological abnormality separated by at least 30 days from onset of a preceding clinical event

*and*

  - b. Neurological abnormality lasting for at least 24 hours
5. Absence of fever or known infection (fever with temperature (axillary, orally or intrauricular) > 37.5°C)
6. Objective neurological impairment, correlating with the subject's reported symptoms, defined as either
  - a. Increase in at least one of the functional system (FS) scores of the EDSS

or

  - b. Increase of the total EDSS score

The occurrence of paraesthesia, fatigue, mental symptoms, and/or vegetative symptoms without any additional symptom will not be classified as an MS clinical relapse.

 The time to sustained progression of disability is defined as the time to a sustained increase (for at least 3 months) of at least 1 point in the EDSS score compared to baseline for all subjects with an EDSS ≤5.0 or an increase of at least 1.5 points if the baseline EDSS score was 0.

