 The time to sustained progression of disability is defined as the time to a sustained increase (for at least 3 months) of at least 1 point in the EDSS score compared to baseline for all subjects with an EDSS ≤5.0 or an increase of at least 1.5 points if the baseline EDSS score was 0.

	
assessment. Assessments schedule is approximate, all described assessments and events will be collected and finally statistician will analyse them within relevant window for respective visit. According to standard practice in Slovakia, patients treated by DMD visit their physician at MS centre at least once per year (as required by payers) but usually every 3 months.
 
Patients will be followed up to 4 years after the first dose of Cladribine 10 mg tablets. Patients with low lymphocyte count to start Cladribine 10 mg tablets therapy after the first year are allowed to postpone second cycle up to 6 months until lymphocyte count recovers (as per SmPC) and therefore their participation may take up to 4.5 years.

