### 6.3.1 Inclusion Criteria

- Age  $\geq$ 18 years.
- Patients for whom start of Cladribine 10 mg tablets therapy for highly active relapsing MS (relapsing-remitting multiple sclerosis – RRMS, or secondary progressive multiple sclerosis - SPMS) has been indicated independently before signing informed consent.
- Patient fulfils following local indication criteria for Cladribine 10 mg tablets treatment as applicable in standard of care:
  - 1 severe relapse treated by corticosteroids or EDSS score increase by at least 1 grade during the previous year and at least 1 T1Gd+ lesion or 9 or more T2 lesions during the treatment by at least one other DMD,
- OR
- 2 or more disability causing relapses treated by corticosteroids during the previous year and treated or untreated by the other DMD. MS diagnosis has to be confirmed by cerebrospinal fluid examination.
- Signed informed consent.
- Ability to communicate with investigator and study staff and to comply with their instructions for the entire length of the study participation

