### 6.3.2 Exclusion Criteria

- Other type of MS than highly active relapsing MS
- Contraindications listed in Cladribine 10 mg tablets SmPC.
- Moderate or severe hepatic impairment (Child-Pugh score  $>$ 6).
- Patient (men and women of childbearing potential) is unable or unwilling to practice birth control during Cladribine 10 mg tablets treatment and for at least 6 months after the last dose.
- Concurrent participation in any interventional study.

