### 7.2 Secondary endpoints

- Proportion of relapse-free patients at 24 and 48 months
- ARR at 24 months
- The time to sustained progression of disability from baseline up to 24 and 48 months
- Time to the first relapse from baseline up to 48 months
- Time to the second relapse from baseline up to 48 months

- Changes in mean number of T1 Gd+ lesions per MRI scan taken at 12, 24, 36 and 48 months compared to baseline
- Changes in mean number of active T2-weighted lesions per MRI scan taken at 12, 24, 36 and 48 months compared to baseline
- Changes in level of disability as measured by EDSS at 6, 12, 18, 24, 30, 36, 42 and 48 months compared to baseline
- No evidence of disease activity (NEDA-3) at 24 and 48 months
- The proportion of patients receiving rescue therapy according to local standards of care from baseline up to 48 months
- Patient adherence to Cladribine 10 mg tablets treatment after both dosing periods as assessed at 3 and 15 months (by counting used tablets from original packages as patients will be asked to bring them to the site).
- Frequency of adverse events interviewed or reported spontaneously by the patients or as noted on physical, MRI or laboratory examinations up to month 48
- Percentage of patients with at least 1 Common Terminology Criteria for Adverse Events (CTCAE) grade 3 or 4 Lymphocyte Toxicity up to month 48
- Median time to recovery from grade 3 or 4 Lymphocyte Toxicity
- Percentage of patients who developed herpes zoster infections or malignancies up to month 48

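### The sustained-progression rule sets no threshold for baseline EDSS above 5.0, although eligibility allows such patients to be enrolled

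*Protocol*

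**What the plan says.** Protocol Section 4.2, footnote 4, holds the only definition of disability progression, and footnote 2 of the synopsis (Section 1) repeats it word for word. The rise must last at least 3 months. Two thresholds are given. The general one is a rise "of at least 1 point in the EDSS score compared to baseline for all subjects with an EDSS ≤5.0". The other is stricter and applies to patients who start the study with a score of zero: "or an increase of at least 1.5 points if the baseline EDSS score was 0". The definition ends there.

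Section 6.3.1 admits both disease courses ("relapsing-remitting multiple sclerosis – RRMS, or secondary progressive multiple sclerosis - SPMS") where highly active relapsing disease is the indication. EDSS enters the inclusion criteria only as recent change, "EDSS score increase by at least 1 grade during the previous year", which is one of several ways to qualify. Section 6.3.2 restricts the type of disease ("Other type of MS than highly active relapsing MS") but not the level of disability.

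Section 7.2 lists time to sustained progression up to 24 and 48 months as a secondary endpoint and does not limit it to a range of baseline EDSS. It also lists "No evidence of disease activity (NEDA-3) at 24 and 48 months" without defining the components.

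**The concern.** A patient with baseline EDSS above 5.0 meets neither clause, so no rise of any size or duration is an event under the rule. Nothing in the eligibility criteria keeps such patients out. The analyst must then do one of three things: keep them as non-events, drop them, or supply a threshold that the protocol does not contain. These choices give different results, and the text does not select one.

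Evaluating the occurrence of progression is the first secondary objective, and Section 3 names relapse and disability progression together as key effectiveness parameters. A rule that cannot register worsening in part of the eligible population weakens that result. It would tend to make it look favourable if the omitted patients are kept as non-events, or if they are dropped and are at higher risk than the rest.

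There is also a smaller wording fault. Baseline 0 lies inside the first clause, which has no lower bound, so both thresholds apply to it.

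**Working it through.** The protocol states no figure that depends on this rule, so there is none to reproduce. The check has two parts.

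**1. Apply the rule to each baseline level.** I read the first clause as referring to baseline EDSS and assume the usual scale of 0, then 1.0 to 9.5 in half-point steps (19 levels).

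| Baseline EDSS | Thresholds that apply as written |
|---|---|
| 0 | 1.0 and 1.5 (both clauses) |
| 1.0 to 5.0 (9 levels) | 1.0 |
| 5.5 to 9.5 (9 levels) | none |

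No event can be defined at 9 of the 19 levels. This counts scale levels and says nothing about how many patients sit at them.

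**2. Illustrate the effect on the proportion with progression.** The protocol gives none of these inputs, so all are assumptions:

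- s, the share of patients with baseline EDSS above 5.0: 5% to 20%
- r, their 4-year progression risk: 30% to 40%
- p, the 4-year risk in the rest: 20%

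Formulas:

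- True proportion = (1 − s)p + s·r
- Kept as non-events: reported = (1 − s)p, so the understatement is s·r
- Dropped: reported = p, so the understatement is s(r − p)

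| | s = 5%, r = 30% | s = 20%, r = 40% |
|---|---|---|
| True | 0.95×0.20 + 0.05×0.30 = 20.5% | 0.80×0.20 + 0.20×0.40 = 24.0% |
| Kept as non-events | 0.95×0.20 = 19.0% | 0.80×0.20 = 16.0% |
| Understatement | 1.5 points | 8 points |
| Dropped | 20.0% | 20.0% |
| Understatement | 0.5 points | 4 points |

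**Sensitivity to the higher-risk assumption.** Set r = p = 20%. Keeping the patients as non-events still understates: with s from 5% to 30%, a true 20% is reported as 0.95×0.20 = 19% down to 0.70×0.20 = 14%. That is 1 to 6 missed events per 100 patients. Dropping them then causes no bias, because s(r − p) = 0. The direction in the dropped case therefore depends entirely on r exceeding p.

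**The case against.** The best defence is that the first clause may be meant to say who is evaluable, in which case patients above 5.0 are simply outside the endpoint. That reading is possible. But the endpoint list in Section 7.2 carries no such restriction, and the protocol nowhere says that these patients are to be excluded or counted. The ambiguity remains, and the reported proportion depends on how it is resolved.

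A second defence is that Section 12 foresees a SAP, which may change evaluated parameters with justification. That is a route to repair. It does not cure the fault, because the protocol itself fixes the numerical rule and leaves it incomplete.

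A third defence stands in full. This is one secondary endpoint in a descriptive, non-interventional study. The primary endpoint, ARR at 48 months, does not use the rule. EDSS change at eight time points covers patients at every baseline level, so worsening above 5.0 is still reported there.

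A reader might also infer more than the documents support:

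- **That such patients will certainly be enrolled, or are the group most likely to worsen.** The protocol gives no EDSS distribution or risk by baseline level, and SPMS is admitted only where disease is highly active and relapsing. It shows only that they can be enrolled.
- **That NEDA-3 is distorted.** Its components are not defined and it does not refer to the footnote. The link holds only if its disability part uses this rule. If it also counts relapse and MRI activity, patients above 5.0 could still fail it on those.
- **That the 1.5-point clause has no effect.** A literal reading allows this, but the clause for baseline 0 is specific and stricter, so it is plainly meant as an exception. This is a drafting fault with clear intent.

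**Conclusion.** The point holds. The protocol's only progression definition is incomplete for a baseline range that its eligibility criteria allow. As written, a patient with baseline EDSS 5.5 or more cannot have a progression event. Kept in the analysis, such patients count as progression-free; dropped, the result no longer describes the enrolled population.

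The effect reaches time to sustained progression at 24 and 48 months, and NEDA-3 conditionally. Its size cannot be determined from the protocol. The illustrative ranges of 1.5 to 8 points (kept) and about 0.5 to 4 points (dropped) rest wholly on the assumed share and risks, and the risk above 5.0 itself depends on a threshold that the protocol does not state. If nobody above 5.0 is enrolled, the effect is nil.

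This should be fixed, but it is not critical: it concerns a secondary endpoint, and ARR and EDSS change are unaffected.

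**What to change.** Before database lock, take one of two routes, with the same text in footnotes 2 and 4:

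1. **Exclusive tiers for every baseline level:** at least 1.5 points if baseline is 0; at least 1.0 point if baseline is above 0 and up to 5.0; and a stated threshold for 5.5 or higher. At least 0.5 point is one example for the last tier. That value does not come from the protocol, so the sponsor should justify whichever it chooses. The 3-month requirement applies throughout.
2. **An explicit restriction** of the endpoint to patients with baseline EDSS 5.0 or below, with the number excluded reported.

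Under either route, state that the disability part of NEDA-3 uses the same definition, and report the number of patients per tier. The tiered wording also removes the overlap at baseline 0.

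The cost is a short change of definition, handled as a protocol amendment or as a justified change in the SAP. No new data are needed, because the flow chart (Table 8-1) already collects EDSS at V1, V3, V4 and V6 through EOS.

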## 5 STUDY DESIGN

### 5.1 Description of the study design

This is a non-interventional, multicentre, prospective study for patients with highly active relapsing MS for whom Cladribine 10 mg tablets therapy was indicated independently before enrolment to the study. It is planned to enrol about 100 patients in 12 sites specialized for MS treatment in Slovakia (for sample size consideration please see Section 12.1).

Eligible subjects will undergo all visits and procedures before and during the treatment as per local standards and Cladribine 10 mg tablets administration will be in accordance with approved SmPC. There is no assessment mandated per study protocol. Management of disease including administration of rescue therapy and visit schedule are fully at the treating physician's discretion. Data for the study will be extracted from medical charts and entered into the electronic Case Report Forms (eCRF). Study assessments schedule (Table 8-1: Flow chart) is approximate, all described assessments and events will be collected and finally statistician will analyse them within relevant window for respective visit. According to standard practice in Slovakia, patients treated by DMD visit their physician at MS centre at least once per year (as required by payers) but usually every 3 months.

To collect high quality adherence data, patients will be asked to bring used/partially used Cladribine 10 mg tablets packages to the next visit after dosing and physicians will record number of actually used tablets, if Cladribine 10 mg tablets are not administered in the participating site as per standard practice.

Patients will be followed up to 4 years after the first dose of Cladribine 10 mg tablets. Patients with low lymphocyte count to start Cladribine 10 mg tablets therapy after the first year are allowed to postpone second cycle up to 6 months until lymphocyte count recovers (as per SmPC) and therefore their participation may take up to 4.5 years.

### 5.2 Study Timelines

Table 5-1: Study Timelines

Milestone	Panned date
First patient first visit	April 2020
Last patient first visit	August 2021 (enrolment period 18 months)
Last patient last visit/Data collection completed	October 2025 (participation takes 48 months, however patients who have to delay their treatment in second year due to low lymphocyte count up to 6 months as per SmPC will take part for up to 56 months)

## 6 SETTINGS

### 6.1 Site Selection

Centres specialized in the care of patients with MS across Slovakia will be selected for study participation. The planned number of study sites is 12.

### 6.2 Recruitment Modalities

Physician will offer participation to all consecutive patients meeting eligibility criteria during the enrolment period. Competitive enrolment is allowed.

## 6.3 Study Population

Planned number of patients in the study is approximately 100.

### 6.3.1 Inclusion Criteria

- Age  $\geq$ 18 years.
- Patients for whom start of Cladribine 10 mg tablets therapy for highly active relapsing MS (relapsing-remitting multiple sclerosis – RRMS, or secondary progressive multiple sclerosis - SPMS) has been indicated independently before signing informed consent.
- Patient fulfils following local indication criteria for Cladribine 10 mg tablets treatment as applicable in standard of care:
  - 1 severe relapse treated by corticosteroids or EDSS score increase by at least 1 grade during the previous year and at least 1 T1Gd+ lesion or 9 or more T2 lesions during the treatment by at least one other DMD,
- OR
- 2 or more disability causing relapses treated by corticosteroids during the previous year and treated or untreated by the other DMD. MS diagnosis has to be confirmed by cerebrospinal fluid examination.
- Signed informed consent.
- Ability to communicate with investigator and study staff and to comply with their instructions for the entire length of the study participation

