### 8.2 Collected Data

#### V1 - Pre-dose Year 1 Visit

Date of visit, date of ICF signature (if different), meeting of eligibility criteria (yes/no)

Basic demographic data:

- Year of birth
- Gender

Baseline characteristics:

- Relevant medical history
- Relevant concurrent diseases/concomitant medications

Condition of MS:

- Date of MS diagnosis
- Medical history related to MS
- Previous MS therapy
- Number of relapses in the last 12 months
- Current EDSS score
- Current MRI status (within 3 months)

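### With no required interval between the last relapse and the V1 EDSS, the reference score can be raised in patients still recovering, which can distort EDSS change and sustained progression

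*Protocol*

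**What the plan says.** **Selection.** Section 6.3.1 of the protocol gives two routes. The first asks for "1 severe relapse treated by corticosteroids or EDSS score increase by at least 1 grade during the previous year", together with an MRI criterion under another DMD. The second asks for "2 or more disability causing relapses treated by corticosteroids during the previous year".

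**Reference score.** Section 8.2 lists "Current EDSS score" at V1, and the flow chart (Table 8-1) shows no other EDSS before dosing. There is no minimum time since the last relapse, no stability condition and no second reading. The MRI item in the same list does carry a 3-month window.

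**History before V1.** The one named relapse item is "Number of relapses in the last 12 months". A general item for MS medical history is also listed, without required content.

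**Endpoints that use the reference.** Section 7.2 has "Changes in level of disability as measured by EDSS at 6, 12, 18, 24, 30, 36, 42 and 48 months compared to baseline". The footnote to section 4.2 defines progression as "a sustained increase (for at least 3 months) of at least 1 point in the EDSS score compared to baseline", or 1.5 points if the baseline was 0. Section 7.2 also has NEDA-3 at 24 and 48 months, without listing its components.

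**Setting.** Section 5.1 describes a single cohort, section 12.2 a descriptive analysis with means and 95% confidence intervals, and section 3 an aim of evaluating the clinical benefit of treatment.

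**The concern.** Patients enter because their disease was recently active, and they are then compared with a score that may still contain part of that activity. The protocol's own relapse definition requires a rise in the total EDSS or in a functional system score, so an EDSS taken during or soon after a relapse can lie above the patient's stable level.

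Two errors can follow, both favourable to treatment. Recovery that would have happened anyway appears as improvement from baseline. A later lasting deterioration has to exceed the raised score by the full threshold before it counts. With no comparator, natural recovery cannot be separated from a drug effect. At stake are two secondary objectives in section 4.2: occurrence of disability progression and change in EDSS.

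**Working it through.** **Figures in the plan.** The protocol states no figure for any EDSS endpoint. Its one related calculation reproduces: 85 / (1 − 0.15) = 100 patients. I use n = 85 below. The values of relapse timing, f, r, SD and progression are assumptions.

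**1. One patient (illustration).** Stable EDSS 3.0, scored 4.0 at V1 during a relapse, back to 3.0 at V3 (6 months after first dose), later permanently 4.0. Against V1 the changes are −1.0 and then 0, so an improvement is shown and progression is never counted. Against the stable level the last change is +1.0, which meets the threshold.

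**2. Threshold.** With an unrecovered deficit r at V1, the worsening needed over the stable level is 1.0 + r: 1.5, 2.0 or 2.5 points for r = 0.5, 1.0 or 1.5.

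**3. Recency.** Assume relapses are uniform over the 12 months before V1 and independent. The share with the last relapse within 3 months is:
- one relapse: 3/12 = 25%
- two relapses: 1 − 0.75² = 44%

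These are shares with a recent relapse. They are not shares with a raised baseline.

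**4. Mean EDSS change.** Let f be the share of the cohort with an unrecovered deficit r at V1. Assume no drug effect, no true change, and full recovery of the deficit afterwards. The mean change is −f·r, with standard error √(SD² + f(1−f)r²)/√85. The chance that the 95% CI lies wholly below 0 is Φ(f·r/SE − 1.96), which is 2.5% without bias. With SD = 1.0:

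| f | r | Mean change | SE | Chance CI is below 0 |
|---|---|---|---|---|
| 10% | 0.5 | −0.05 | 0.110 | 7% |
| 25% | 1.0 | −0.25 | 0.118 | 56% |
| 50% | 1.0 | −0.50 | 0.121 | 98% |

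For the middle row, SD = 1.25 gives 41% and SD = 0.75 gives 76%.

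**5. Missed progression.** Assume true progression of 20% at 48 months, with worsening of 1.0, 1.5 or 2.0 points in 50%, 30% and 20% of progressors. The share missed is f × P(worsening < 1.0 + r):
- f = 10%, r = 0.5: 0.10 × 0.50 = 5% missed, so 20% is seen as 19%
- f = 25%, r = 1.0: 0.25 × 0.80 = 20% missed, so 20% is seen as 16%
- f = 50%, r = 1.0: 0.50 × 0.80 = 40% missed, so 20% is seen as 12%

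A simulation of 400,000 patients gave the same results.

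**The case against.** The other side has several good points.

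- **Not every selected patient has a raised baseline.** An EDSS rise in the previous year may be permanent, and SPMS patients are eligible; for a permanent rise V1 is the true level. A recovered relapse also leaves nothing behind. A reader might infer that the selection rule in itself biases the results. The documents support only that it can. This stands.
- **Relapse timing may be recoverable.** Sites must place qualifying events within the previous year, charts are the source, and dates may be entered under MS medical history. A reader might infer that a relapse-affected V1 score can never be recognised. That goes too far; what holds is that no named item assures the date.
- **The 25% and 44% measure recency.** Reading them as shares with inflated baselines, or as conservative, has no support in the protocol. The steps before treatment in section 8.2 (infection screening, postponement for vaccination, the contraindication for current immunosuppressive therapy) may lengthen the gap after a relapse, though none of them sets an interval for the EDSS.
- **Limited reach.** The primary ARR does not use baseline EDSS, NEDA-3 components are not defined in the protocol, and the analysis is descriptive. All true, and this limits the weight of the point.
- **Supportive analyses belong to the SAP.** Largely so, and their absence from the protocol is no error. But an SAP approved shortly before database closure cannot guarantee a date that the data collection never required.
- **Eligibility follows a national prescribing limitation.** Correct, so the remedy should lie in measurement and analysis and leave eligibility alone.

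**Conclusion.** The point holds as a possible bias in secondary endpoints. The protocol selects on recent worsening, takes the EDSS at V1 without any interval from the last relapse, and measures change and progression from that score in a cohort without a control. In patients with an unrecovered deficit at V1, this can overstate improvement and understate progression.

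The size cannot be read from the document. Under the stated assumptions it runs from minor (mean change −0.05; 20% progression seen as 19%) to seriously misleading (mean change −0.50; 20% seen as 12%). Where the study falls depends on f and r. As collected, the study may be unable to tell, because the date of the last relapse is not assured.

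A reader might go further and conclude that every statement of improvement should rest on the V3 score. That does not follow: a V3 reference would discard real change in the first 6 months on treatment. The point is worth acting on because the remedy is cheap, and it does not call the primary analysis into question.

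**What to change.** 1. In section 8.2, make the onset date of the last relapse before V1 a named V1 item. Allow for none, since the first eligibility route can be met by an EDSS rise alone.
2. Keep the V1-referenced analysis as the main one.
3. Add supportive results: (a) EDSS change and sustained progression split by last relapse within 3 months of V1 versus earlier; (b) sustained progression with the V3 EDSS as reference, in patients whose last relapse began within 3 months before V1. If NEDA-3 is defined to include EDSS progression, note that it shares the limitation.
4. State that improvement from V1 in recently relapsed patients cannot be attributed to treatment.

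**Cost.** One date from the chart and supportive tables on EDSS scores already collected. Eligibility, care and the visit schedule stay as they are, and no assessment becomes mandatory. The V3-referenced version misses change between V1 and V3 in either direction and loses patients with no V3 EDSS, so it should appear only beside the V1-referenced result.
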